## Additional Secondary Outcomes

- Mortality rate over 2.5 years by subgroups:
  - Region (Dosso, Tahoua, Maradi, Zinder, and Tillabéri)
  - Child age (1-11m, 12-24m, 24-59m)
  - Child sex
  - Community distance to the nearest Centre de Santé Intégré (CSI)
  - Number of previous community distributions
  - Timing of distribution/seasonality
  - Other interventions
    - Participation in MORDOR trials
    - Participation in and coverage of Seasonal Malaria Chemoprevention (SMC)
    - Participation in trachoma distributions of azithromycin
  - Nutritional status as defined by weight, MUAC, height interval
- Program costs as captured by routine administrative data collection during the study period and by micro-costing activities (T&M)
  - *Measured cost per dose* of azithromycin MDA in Niger for the two age groups (1 – 11 months of age and 1 – 59 months of age)
  - *Variation in measured cost per dose* of azithromycin MDA as a function of community characteristics.
  - *Modeled cost per dose* of an azithromycin MDA in new but similar settings. Values will be assigned to each *input cost category* (personnel, consumables, equipment, services, training, space), *activity* (eg, publicity, transport), and level (communities / household / child) using a fixed and variable cost perspective adjusted to the level, and adjusted for community-level characteristics.
  - Total observed azithromycin MDA program costs, by age group (1 – 11 month versus 1 – 59 month)
- Cost-effectiveness measured by estimated program costs and using measured mortality and estimated DALYs as the effectiveness outcome, compared across arms.
  - ICER for administering azithromycin to the different age groups, comparing the cost and effectiveness of 1 – 59 month vs. 1-11 month.

- Estimated 10 year national-scale effects (health and cost) of scaling up each strategy.
- Other implementation outcomes defined in the Proctor Outcomes Framework,[8] including feasibility and acceptability, as captured during routine administrative and monitoring data collection during the study period and by stakeholder interviews at the participant, community, and health system levels at 2.5 years (Table 3).
- Change in nutritional status over time as defined by weight, mid-upper arm circumference (MUAC), and height interval
- All-cause clinic visits among children 1-59 months of age in the study area during the study period as assessed through passive surveillance of Centre de Santé Intégré records.
- Cause-specific clinic visits among children 1-59 months of age in the study area during the study period as assessed through passive surveillance of Centre de Santé Intégré records, including visits with diagnoses of respiratory infection, diarrheal disease, and malaria.
- Respiratory microbiome by arm in all age groups (children 1-59 month old, children 7-12 year old and caregivers/guardians) as specified microbiome substudy primary outcomes

## Other Outcomes

- Cause-specific mortality by treatment arm as defined by verbal autopsy\* over 2.5 years
- Serology outcomes as assessed by dried blood spots during sample collections at baseline and 24 months
- Normalized read number of genetic determinants of resistance by antibiotic class in environmental samples at baseline and 24 months

\*Depending upon resources, verbal autopsy might be conducted by UCSF or another group

## MORDOR trial subgroup continuation outcomes

The AVENIR trial will include the 594 villages in Dosso region that were previously enrolled in the MORDOR I, II and III trials. This creates an opportunity to study the longer-term effects of mass azithromycin treatment on and on antimicrobial resistance.

- Longer-term carry-over effects on mortality
  - MORDOR III, beginning at month 42, re-randomized villages to receive bi-annual mass distribution of azithromycin or placebo to children 1-59 months, and followed the communities for 18 additional months (in three inter-census intervals 42-48m, 48-54m, 54-60m). From MORDOR communities allocated to the placebo arm of AVENIR, we will compare the mortality rate among children ages 1-59 months over 2.5 years in communities that received azithromycin during MORDOR III versus those that received placebo during MORDOR III. Our primary comparison of interest is among communities allocated to AVENIR's placebo arm because it will enable us to study longer-term carry-over effects of previous azithromycin treatment after discontinuation. We hypothesize

that communities that previously received azithromycin during MORDOR phase 3 will have lower mortality compared to communities that continually received placebo for the entire period. The analysis approach will follow the primary analysis, estimating incidence rate ratios using a negative binomial regression. Comparisons within additional AVENIR arms (1-59m, 1-11m) could be estimated as an exploratory analysis.

- Longer-term carry-over effects on antimicrobial resistance
  - During MORDOR III, 160 communities were tested for genetic determinants of antimicrobial resistance at month 54. This creates the opportunity to study effects of treatment history on longer-term effects for antimicrobial resistance selection. From the 160 communities in the MORDOR trial with resistance measures, the AVENIR trial will randomly select 40 communities, evenly distributed (20/20) between two treatment histories (AAAAA, AAAPP, each letter refers to a year of Azithromycin or Placebo). Within each community, we will collect a rectal swab from 30 children 1-59 months, and test the samples for genetic determinants of antimicrobial resistance using metagenomic deep sequencing, as in the resistance primary analysis. This additional substudy will enable two analyses of primary interest:
    - At enrollment in AVENIR, approximately 1 year after the end of MORDOR, we will compare the load of genetic determinants of antimicrobial resistance to macrolides (primary) and other classes of antibiotics (secondarily) between the two treatment histories. We hypothesize that load of genetic determinants will be higher among communities with the AAAAA history compared with AAAPP history. The analysis approach will follow the primary analysis for the antimicrobial resistance substudy
    - Among the 20 communities with AAAPP treatment history in MORDOR, we will compare the the load of genetic determinants of antimicrobial resistance to macrolides (primary) and other classes of antibiotics (secondarily) longitudinally over time from MORDOR 54 to AVENIR enrollment (approximately 1 year later), and again to the final measurement in AVENIR phase 1 (approximately 3 years after discontinuation of azithromycin). We hypothesize that load of genetic determinants will decline with time from last treatment.

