4.4. Mortality/Resistance Trial

4.4.1. Trial Design

In the Mortality Trial, communities in the Dosso region in Niger will be randomized in a 1:1:1 fashion to: **1) azithro 1–11**: biannual azithromycin to children 1–11 months old with placebo to children 12–59 months old, **2) azithro 1–59**: biannual azithromycin to children 1–59 months old, or **3) placebo**: biannual placebo to children 1–59 months old. For regions enrolled after the one-year run-in period, the randomization allocation will be updated based on the probability of mortality in children 1–59 months in each arm. Communities will retain their allocation for 4 distributions. A dedicated study team will conduct a biannual door-to-door census to deliver the intervention and monitor mortality. Within the Mortality Trial, 150 communities in the Dosso region will be randomly selected from among the eligible communities, similarly randomized 1:1:1, and followed to monitor antimicrobial resistance (Figure 1).

The initial design compares the efficacy of different age-based azithromycin distribution strategies to reduce child mortality. After the primary outcome analysis additional treatment arms may be added to the trial or arms may be dropped from the trial. With such changes, protocol details, power calculations, and analysis plans will be updated accordingly in the protocol and statistical analysis plan.

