4.4.5.2. Sample Collections

150 of the communities in the Mortality Trial in the Dosso region will be randomly selected to be followed to monitor antimicrobial resistance. In each community, 30 children aged 1–59 months, 30 children 7–12 years, and 30 caregivers/guardians of eligible children will be randomly selected for sample collections at baseline and after 4 distributions. Samples will be collected in a random subset of 60 communities at baseline, and in all 150 AMR communities after 4 rounds (approximately 2 years).

An additional 40 communities that participated in the MORDOR 54 trial will be randomly selected for inclusion in sample collections at baseline. Of these 40 communities, 20 will be randomly selected from among those who received 5 rounds of azithromycin during MORDOR, and the other 20 communities be randomly selected from among those who received 3 rounds of azithromycin and 2 rounds of placebo during MORDOR. In each community, 30 children 1–59 months will be randomly selected to receive a rectal swab.

Furthermore, 60 communities whose children aged 1–59 months have received ~11 biannual

distributions of azithromycin (as opposed to placebo) during the MORDOR trial will be selected randomly: 20 randomized in AVENIR to two more years of biannual azithromycin to 1-59 month olds, 20 randomized to biannual azithromycin to 1-11 month olds, and 20 randomized to biannual placebo. 40 children per grappe, aged 1-59 months, will be randomly selected from the prior census. Examiners will perform a nasopharyngeal swab on each child, stored in STGG media.

In all communities selected for sample collections, treatment distribution for that round will be conducted after sample collections.

Refer to SAP for details of power calculations.

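### The last step of the AAAPP resistance-decay analysis pools communities that AVENIR is expected to put back on azithromycin; it should be limited to AVENIR placebo communities or dropped

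*SAP*

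**What the plan says.** The MORDOR continuation part of SAP section 3.5.1 lists a longitudinal resistance analysis as one of two of main interest in that substudy. Its population is "Among the 20 communities with AAAPP treatment history in MORDOR". Load is compared "from MORDOR 54 to AVENIR enrollment (approximately 1 year later") and then "again to the final measurement in AVENIR phase 1 (approximately 3 years after discontinuation of azithromycin"). The stated expectation is: "We hypothesize that load of genetic determinants will decline with time from last treatment". No restriction, stratification or adjustment by AVENIR arm is given.

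The same part of the SAP states: "The AVENIR trial will include the 594 villages in Dosso region that were previously enrolled in the MORDOR I, II and III trials". Under Protocol 4.4.1, "communities in the Dosso region in Niger will be randomized in a 1:1:1 fashion to" azithro 1–11, azithro 1–59 or placebo. Protocol 4.4.3.2 keeps Dosso communities in their arm for the whole first stage.

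For the parallel mortality carry-over question the SAP does restrict by arm: "Our primary comparison of interest is among communities allocated to AVENIR's placebo arm because it will enable us to study longer-term carry-over effects".

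On sampling, Protocol 4.4.5.2 says: "An additional 40 communities that participated in the MORDOR 54 trial will be randomly selected for inclusion in sample collections at baseline". It names no later collection for them.

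**The concern.** An analysis of decay after stopping needs communities that stay off the drug. Two of the three AVENIR arms give azithromycin, so many of the 20 communities would resume distributions between the second and third measurements. Load that rises or fails to fall because of renewed treatment could then be read as resistance persisting after treatment stopped. The SAP applies the needed restriction to mortality a few lines earlier but not here.

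Two related points affect the same time point. The 3-year label does not match the time since last azithromycin that the AAAPP history implies, and the protocol does not clearly provide for the swab. At stake is the interpretation of this one substudy comparison.

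**Working it through.** **Inputs**
- 20 AAAPP communities; letters coded as years; MORDOR III running from month 42 to month 60; AVENIR enrollment about 1 year after month 54 in one bullet and about 1 year after the end of MORDOR in another (SAP 3.5.1).
- Final AMR measurement 24 months after baseline (SAP 3.2.7).
- Allocation 1:1:1 in Dosso, retained through the first stage (Protocol 4.4.1, 4.4.3.2).
- In azithro 1–11, children 12–59 months receive placebo (Protocol 4.4.3.1).
- About 5 children aged 12–59 months per child aged 1–11 months (Protocol section 2).
- Where samples are taken, that round's treatment follows the sampling (Protocol 4.4.5.2).

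**Step 1: reproduce the 3 years.** Elapsed years = (enrollment month + 24 − anchor month)/12. Enrollment falls at month 54 + 12 = 66 or 60 + 12 = 72.

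| Anchor | Enrollment at 66 | Enrollment at 72 |
|---|---|---|
| MORDOR 54 | 3.0 | 3.5 |
| End of MORDOR (60) | 2.5 | 3.0 |
| MORDOR III start (42) | 4.0 | 4.5 |
| End of third azithromycin year (36) | 4.5 | 5.0 |
| Letters read as six-month rounds (60 − 12 = 48) | 3.5 | 4.0 |

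Three years is reproduced only from MORDOR 54 or the end of MORDOR. By then AAAPP communities were already on placebo. With letters as years, time since last azithromycin is about 4 to 5 years. Protocol 4.4.5.2 describes the same histories in rounds; if a round is taken as six months (an assumption), the result is 3.5 to 4 years.

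**Step 2: arms of the 20.**
- Azithromycin-containing arm: 20 × 2/3 = 13.3 expected; binomial 95% range 9 to 17.
- Each single arm: 20 × 1/3 = 6.7 expected; range for placebo 3 to 11.
- Chance that all 20 are on placebo: (1/3)^20 ≈ 2.9 × 10⁻¹⁰.

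In azithro 1–11, about 1/(1 + 5) = 1/6 of children aged 1–59 months are eligible for azithromycin at any one round. Over the 20 communities, the eligible share of children is 1/3 × 1 + 1/3 × 1/6 = 39%. Because distributions are six-monthly and treatment follows sampling within a round, the last azithromycin in the active arms would be about 6 months before a 24-month swab.

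**Step 3: direction of bias.** Let the log-load change from enrollment to the last point be d in placebo communities, d + r₁ in azithro 1–11 and d + r₂ in azithro 1–59. With equal expected thirds, the pooled change is d + (r₁ + r₂)/3. Protocol Aim 2b hypothesizes higher load in the azithromycin arms, so r₁ and r₂ are expected to be positive and the pooled estimate understates decline. The documents give no value for r₁ or r₂ in these communities. As an assumption only, take the 1.4-fold between-arm difference in the SAP's AMR sample-size section. If it applies to azithro 1–59 alone, the pooled fold change is inflated by 1.4^(1/3) = 1.12; if to both arms, by 1.4^(2/3) = 1.25.

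**Step 4: does the third sample exist?** Protocol 4.4.5.2 places the 40 communities (20 of them AAAPP) in baseline collections only. Protocol 4.4.2 excludes MORDOR communities from population-based sampling. Protocol 4.4.8.3 ends by applying the same procedures to communities added from MORDOR. The revision history ties that sentence to a separate group of 60 communities, whose nasopharyngeal sampling is set out in Protocol 4.4.5.2. The 24-month rectal swab therefore has no clear protocol basis.

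**Step 5: precision after restriction (illustration).** Borrow SD 3.1 (natural log assumed), ICC 0.02 and 30 swabs from the SAP's rectal-load calculation. The variance of a community mean is 3.1² × (1 + 29 × 0.02)/30 = 0.506. For n communities with correlation ρ between their two means, SE = √(2 × 0.506 × (1 − ρ)/n), and the detectable fold change is exp[(1.96 + 0.84) × SE] at two-sided 0.05 and 80% power. For ρ from 0.5 to 0 this gives 1.6 to 1.9 with 20 communities and 2.1 to 2.9 with 7.

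**The case against.** The best defence is that the SAP's wording (time since discontinuation, time from last treatment) makes sense only for untreated communities. On that view a qualifier was simply left out, and the placebo restriction on the mortality analysis shows the intent. That is plausible, but the text names all 20 communities, and an analyst following it would pool them.

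Several limits on the point stand:
- **A reader might infer that the last time point cannot show decay at all.** The documents do not support this. About 7 placebo communities are expected and could show it. Re-treatment works against the hypothesized decline, so a decline seen in the pooled set would still be evidence.
- **A reader might infer that two thirds of the communities are fully re-treated.** Community-wide re-treatment is expected in about one third. In another third only infants receive azithromycin. The actual arms of the 20 are not given.
- **A reader might infer one correct elapsed time, such as 4.5 to 5 years.** The documents conflict on years versus rounds and on the enrollment anchor, so no single replacement figure is established.
- **The mixing arises only if a 24-month rectal swab is taken.** The protocol does not clearly schedule one.

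**Conclusion.** The point holds for the last comparison only. As written, that comparison pools communities in which, in expectation, 13.3 of 20 (95% range 9 to 17) are in an azithromycin-containing arm beforehand. It therefore does not isolate change with time off treatment and leans toward apparent persistence. This rests on three assumptions: the 20 follow the 1:1:1 Dosso allocation, azithromycin raises load as Aim 2b expects, and the 24-month swab is collected.

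The 3-year label is wrong as time since last azithromycin under the year coding (about 4 to 5 years) and fits only as time since MORDOR 54 or the end of MORDOR. The SAP and the protocol disagree on whether the third sample is taken.

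The MORDOR 54 to enrollment comparison is unaffected. A reader might infer a threat to the trial's resistance objective or to policy on stopping distributions. The documents do not support that: the AMR primary outcomes use the separate 150-community sample, no document ties this 20-community analysis to such policy, and the primary mortality outcomes are untouched.

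**What to change.** Amend SAP 3.5.1, and the protocol where needed:
1. Limit the last comparison to AAAPP communities allocated to AVENIR placebo, as the mortality carry-over analysis does. State that about 7 are expected. Report the azithro 1–11 and azithro 1–59 communities separately by arm.
2. Define the anchor for elapsed time. If it is last azithromycin, replace the 3-year label once the year coding in the SAP and the rounds wording in Protocol 4.4.5.2 have been reconciled. If it is MORDOR 54 or the end of MORDOR, say so and do not call it discontinuation.
3. Reconcile the final measurement with Protocol 4.4.5.2 and 4.4.2. If no 24-month rectal swab is taken in these communities, delete the third time point and end the analysis at AVENIR enrollment.

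If the swab is already planned, this changes wording only. The cost is precision: the last comparison rests on about 7 communities instead of 20 (illustrative detectable fold change 2.1 to 2.9 instead of 1.6 to 1.9), or is lost. The precision given up belongs to a mixed quantity, not to decay after stopping.

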### 3.5.2. Analysis methods

#### Mortality in the mortality/resistance trial

Our parameter of interest for comparisons of mortality between arms is the relative reduction in mortality measured by the incidence rate ratio (IRR). The primary analysis will be a Poisson regression that includes the count of deaths as the outcome and the community-level person-time at risk as an offset, with observations for each community's inter-census interval. The model will include an indicator variable for each active treatment arm. The adaptive allocation will be accounted for using pooled regression, including in the model additional indicator variables for each of three allocations in the trial (the initial, equal allocation plus 2 adaptations). For community  $i$  and randomization  $j$  ( $j = 1, 2, 3$ ), the model will be:

$$\log(Y_{ij}) - \log(T_{ij}) = \alpha + \beta A_{ij} + \sum_{j=2}^3 \gamma_j P_j,$$

where  $Y_{ij}$  is the number of deaths and  $T_{ij}$  is the person-time at risk in that community;  $A_{ij}$  is a treatment indicator that will vary by each comparison (details below), and  $P_j$  is an indicator for the two adaptive random allocations (the first equal allocation is the omitted category). We will

estimate 95% confidence intervals for the IRRs using bootstrap resampling (10,000 replicates) that resamples communities with replacement and re-estimates the IRRs.

For primary outcome 1 that compares mortality among 1-59 month olds, we will include in the analysis children ages 1-59 months in the 1-59 month treatment arm and placebo arm.  $A_{ij}$  will be an indicator of allocation to the 1-59 month treatment arm, and  $\exp(\hat{\beta})$  will estimate the IRR.

For primary outcome 2 that compares mortality among children ages 1-11 months, we will subset the analysis to children ages 1-11 months enrolled in the 1-11 month treatment arm and placebo arm.  $A_{ij}$  will be an indicator of allocation to the 1-11 month treatment arm, and  $\exp(\hat{\beta})$  will estimate the IRR.

Similarly, for primary outcome 3 that compares mortality among children ages 12-59 months, we will subset the analysis to children ages 12-59 month in the 1-11 month treatment arm and 1-59 month treatment arm.  $A_{ij}$  will be an indicator of allocation to the 1-59 month treatment arm, and  $\exp(\hat{\beta})$  will estimate the IRR.

Secondary mortality analyses will be estimated similarly from the model subset to the appropriate age range.

We will estimate permutation  $P$ -values for each comparison using a randomization test that permutes community treatment labels within each adaptive allocation group according to the probabilities used in each allocation, holding community outcomes fixed, and will assess statistical significance using the fixed sequence, hierarchical testing procedure described above in section 3.3.

We will examine effect heterogeneity by pre-specified effect modifiers on additive and multiplicative scales [10]. We will do so by including interaction terms between effect modifiers and treatment indicators in the regression models.

### Antimicrobial Resistance Substudy

The primary analysis for resistance outcomes from nasopharyngeal swabs will be ANOVA to compare the community-level proportion of individuals with any macrolide resistant genetic determinants across the three arms. The primary analysis for rectal swabs will be ANOVA to compare community-level mean load of macrolide resistant genetic determinants across the three arms. For both sets of swabs, secondary analyses examining resistance in other classes of antibiotics and other age groups will be conducted similarly.  $P$ -values for all resistance analyses will be computed using a permutation test, using a step down minP procedure to control for three pairwise comparisons in each primary outcome, and using a Benjamini-Hochberg correction to control the false discovery rate across additional (non-macrolide) endpoints, described above in section 4.1.

### 3.5.3. Missing data

Individuals with missing outcome data are assumed to contribute one half of one phase of person time to the denominator, and no counts to the numerator. Individuals are counted for each phase in which they are confirmed present at the beginning of that phase.

Communities that completely drop out during a phase will be reported, but their measurements in that phase will not contribute to the primary analysis. Earlier inter-census

intervals to which communities contributed complete data will be included in the primary analysis.

